6.3.1 Study Duration

Patients who attain a CR/VGPR/PR may elect to stop treatment at any point after cycle 2 and proceed to stem cell mobilization and transplantation. Patients who achieve less than a CR/nCR or patients, or who do not proceed to SCT, may receive up to 8 cycles of the combination therapy. Patients who progress will be removed from therapy. If a patient in CR/nCR/VGPR then patients receive up to 2 cycles beyond best response or up to 8 cycles at physician discretion and then proceed to maintenance therapy.

After 8 cycles, patients who have stable or responding disease to treatment and have an acceptable toxicity profile will be allowed to continue treatment on a maintenance schedule described below until disease relapse, unacceptable toxicity, withdrawal of consent or no further clinical benefit is experienced. Doses of thalidomide, lenalidomide, or dexamethasone may be interrupted or reduced in an attempt to manage toxicity at physician discretion.

6.3.2 Dose Delays

Therapy may be held at physician discretion and can continue on study drug when recovered from toxicity as long as they are benefitting from the trial.

6.3.3 Retreatment Criteria

Subsequent cycle of therapy will be initiated when non hematology toxicity have recovered to Grade 1 or baseline. Hematology parameters to redose:

- ANC > 500.
- **Platelet count > 50,000 cells/mm³ for patients with < 50% of bone marrow plasma cells and platelet count > 25,000 cells/mm³ for patients in whom > 50% of the bone marrow nucleated cells were plasma cells.**

6.4 Maintenance Therapy

Maintenance therapy consists of lenalidomide at the dose level tolerated at the completion of cycle 8 and thalidomide at 50 mg daily. Dexamethasone may be continued in the maintenance phase at physician discretion. Patients unable to tolerate either lenalidomide or thalidomide in combination during the maintenance phase may continue on either agent at the investigators discretion.

6.5 Screening

The following screening procedures must be performed within 28 days prior to study entry:

- Subjects who are potentially eligible for study participation must sign an informed consent form prior to the undertaking of screening procedures for this study.
- Inclusion and exclusion criteria are reviewed and documented .
- Multiple myeloma diagnosis will be confirmed and the stage at original diagnosis according to the International Staging System (ISS) and current disease status will be documented if data is available.
- Complete medical history will be obtained to include documentation of all treatments given for multiple myeloma and all concomitant medications used in the prior 4 weeks.
- Physical examination to include measurement of vital signs, height, weight.
- 12-lead ECG
- Directed neurologic examination will be performed, and questioning for symptoms of paresthesia and numbness.
- Clinical laboratory tests: Blood chemistry [sodium, potassium, chloride, CO₂, calcium, magnesium, phosphorus, blood urea nitrogen (BUN), creatinine, glucose, albumin, total protein, alkaline phosphatase, total bilirubin, aspartate transaminase (SGOT/AST), glutamic pyruvic transaminase (SGPT/ALT), lactate dehydrogenase (LDH), B2-microglobulin
- Hematology: hemoglobin, hematocrit, white blood cell (WBC) count and differential, and platelet count.
- Serum or urine pregnancy tests (sensitivity of at least 50 mIU/mL), for females of childbearing potential (WCBP) must be completed. The first test should be performed within 10 – 14 days, and the second test within 24 hours prior to initiation of lenalidomide. Appendix A for more details and for the definition of females of childbearing potential in use for this trial.
- Serum sample for FreeLite™ Testing.
- M component quantification by immunoelectrofixation from serum (SPEP) and 24 hour urine collection for paraprotein measurement (UPEP), SIFE, and UIFE
- Bone marrow aspiration and biopsy to be evaluated for morphology and for cytogenetics by standard banding and FISH (suggested probes include, at a minimum del 13q14, t(4,14), t(14,16), and del 17p).
- Skeletal survey by roentgenograph for quantification of bone lesions with magnetic resonance imaging (MRI) and CT scans as clinically indicated.
- Multiple-symptom assessment tool.
- Serum Cytokines

6.6 Patient enrollment and Registration

Patients are to be registered by the research coordinator. The checklist will be verified and a subject number will be assigned.

6.7 On-study evaluations

Subjects who meet eligibility criteria will be enrolled into the study, and will be assigned a patient number.

Cycle one patients will be followed weekly on Cycle 1, Day 8, 15, 22 (+/- 3 days):

- Clinical laboratory tests: Blood chemistry [sodium, potassium, chloride, CO₂, calcium, magnesium, phosphorus, blood urea nitrogen (BUN), creatinine, glucose, albumin, total protein, alkaline phosphatase, total bilirubin, aspartate transaminase (SGOT/AST), glutamic pyruvic transaminase (SGPT/ALT), lactate dehydrogenase (LDH)
- Hematology: hemoglobin, hematocrit, white blood cell (WBC) count and differential, and platelet count.
- Symptom directed physical examination/vitals

Day 1+/- 7 days of each cycle of therapy (starting with cycle 2):

- Standard myeloma restaging studies including SPEP, UPEP, Free Light Chain measurements (SIFE, UIFE and Bone Marrow biopsy will be done at time of suspected complete remission to document complete remission). MRI and skeletal surveys will be done as clinically indicated to follow the disease.
- Directed neurologic examination will be performed, and questioning for symptoms of paresthesia and numbness.
- Physical Examination
- Clinical laboratory tests: Blood chemistry [sodium, potassium, chloride, CO₂, calcium, magnesium, phosphorus, blood urea nitrogen (BUN), creatinine, glucose, albumin, total protein, alkaline phosphatase, total bilirubin, aspartate transaminase (SGOT/AST), glutamic pyruvic transaminase (SGPT/ALT), lactate dehydrogenase (LDH)
- Hematology: hemoglobin, hematocrit, white blood cell (WBC) count and differential, and platelet count.
- 12 lead EKG
- Patients will be evaluated for AEs at each visit with the NCI CTCAE v3.0 used as a guide for the grading of severity.
- Multiple-symptom assessment tool (also known as the MDASI).
- Blood sample for Serum Cytokines every even cycle.

An unscheduled visit can occur at any time during the study. Source must be maintained for these unscheduled visits.

Multiple-symptom assessment tool (Also known as MDASI)

Symptoms will be measured by the MM module of the MDASI (MDASI-MM). The MDASI is a multiple-symptom measure of cancer-related symptoms (Cleeland et al., 2000) that is sensitive to disease and treatment changes (Cleeland et al., 2004). This instrument is brief, easily understood, and validated in the cancer population. Patients rate the intensity of physical, affective, and cognitive symptoms on 0–10 numeric scales, ranging from “not present” to “as bad as you can imagine.” Patients also rate the amount of interference with daily activities caused by symptoms on 0–10 numeric scales, ranging from “did not interfere” to “interfered completely.” The MDASI-MM has 6 additional items known to be important in assessing patients with MM or MM therapies (constipation, diarrhea, rash, muscle weakness, mouth or throat sores, and poor concentration). The MDASI-MM takes less than 5 minutes to complete. Symptom severity and interference will be the variables of primary interest.

Serum Cytokines

Serum will be obtained on day 1 of each even cycle for measurements of proinflammatory and anti-inflammatory cytokines to correlate to symptom measurements using the MDASI.

Five milliliters of blood will be drawn by vacutainer system into red-top tubes without anticoagulant. Next, the tube will be removed from the refrigerator, and spun at 2000 rpm for 10 minutes at room temperature. The serum is aspirated with a sterile disposable Pasteur pipet and 0.5-mL aliquots are dispensed into each of 3 Nunc (or equivalent) 1-mL cryopreservation tubes. The tubes are labeled with subject’s study number, date of phlebotomy, volume of serum in tube, initials of phlebotomist, and date. The location of the tube in the freezer will be recorded.

Cytokines to be measured include proinflammatory and anti-inflammatory cytokines including IL-1ra, IL-2, IL-6, TNF-a, sTNF-R1, and sTNF-R2 (Lee et al., 2004), the acute-phase response protein CRP, and a transcriptional factor (p50/p65 of NF-kB) that has been appreciated as a factor regulating IL-6 expression *in vivo* in an MM cell line study (Chiang & Stadtmauer, 2004).

The most commonly used assay to measure cytokines is the enzyme-linked immunosorbent assay (ELISA). However, this assay requires a significant volume of sample that may not always be available due to clinical

concerns and institutional guidelines for the maximum volume of blood that can be drawn for research purposes from a patient over a defined period of time. To address this issue, we have implemented another assay system, the flow cytometry-based Luminex Multiplex Cytometric Bead Array (Multiplex) assay, which requires little serum. In addition, the advantage that the Multiplex has over the ELISA is its ability to measure up to 25 cytokines in one run using a single sample, thereby providing relative concentrations among 25 cytokines and also minimizing the variance of the data. However, in some instances, the Multiplex assay may not be as sensitive as a high-sensitivity ELISA, which requires twice the volume of sample as routine ELISA.

Cellular studies for NFκ-B expression: synthesis of cytokines and/or NF-κB expression by individual peripheral blood leukocytes (lymphocytes and monocytes) will be measured by flow cytometry. Specifically, we will measure the synthesis of IL-6, IL-10, IL-1β, and normal leukocytes using 3- or 4-color flow cytometry methods. Leukocytes from peripheral blood specimens will be cryopreserved for batch analysis at a later date.

Peripheral blood mononuclear cells (PBMC). At baseline and at the beginning of every even cycle PBMC will be isolated from 10 mL of peripheral blood drawn into a green-top tube using density gradient centrifugation (Ficoll-Hypaque) separation. Next, the PBMC pellet will be lysed for determination of active NFκB using the ELISA-based assay for NFκB p50 and p65 (Strassgen, Ann Arbor, MI). The assay is developed with a chemiluminescent substrate and the manufacturer-recommended procedure will be followed to obtain reliable assay results.

Maintenance Therapy Study Visits

Once a month during Maintenance Therapy, the following tests and procedures will be performed:

- Standard myeloma restaging studies including SPEP, UPEP, Free Light Chain measurements (SIFE, UIFE and Bone Marrow biopsy will be done at time of suspected complete remission to document complete remission)
- Clinical laboratory tests: Blood chemistry [sodium, potassium, chloride, CO₂, calcium, magnesium, phosphorus, blood urea nitrogen (BUN), creatinine, glucose, albumin, total protein, alkaline phosphatase, total bilirubin, aspartate transaminase (SGOT/AST), glutamic pyruvic transaminase (SGPT/ALT), lactate dehydrogenase (LDH)
- Hematology: hemoglobin, hematocrit, white blood cell (WBC) count and differential, and platelet count.

End-of-Study Visit

If you go off study for any reason, you will have an end-of-study visit. This is usually done about 30 days after the last dose of the study drugs. At this visit, the following tests and procedures will be performed:

You will have a physical exam, including measurement of your vital signs and weight.

- Standard myeloma restaging studies including SPEP, UPEP, Free Light Chain measurements (SIFE, UIFE and Bone Marrow biopsy will be done at time of suspected complete remission to document complete remission)
- Clinical laboratory tests: Blood chemistry [sodium, potassium, chloride, CO₂, calcium, magnesium, phosphorus, blood urea nitrogen (BUN), creatinine, glucose, albumin, total protein, alkaline phosphatase, total bilirubin, aspartate transaminase (SGOT/AST), glutamic pyruvic transaminase (SGPT/ALT), lactate dehydrogenase (LDH)
- Hematology: hemoglobin, hematocrit, white blood cell (WBC) count and differential, and platelet count.

Follow-Up

Subjects who discontinue treatment for any reason, will be followed for 30 days. At treatment discontinuation, subjects will undergo a safety assessment approximately 30 days post the last dose of study drug.

Treatment is to be continued and patients will be followed until progression of disease. Patients eligible for and wishing to pursue stem cell transplant will receive at least 2 courses of therapy and will be followed until stem cell transplant, progression of disease, or treatment failure.

Treatment failure will be defined by progression of disease.

Response and progression will be evaluated in this study using the International uniform response criteria for multiple myeloma (Appendix D).

6.8 Drug Administration

6.8.1 Lenalidomide Administration

For all cycles, lenalidomide will be given as a single daily oral dose on Days 1-21 followed by 7-day rest period. The dose will be specified for each cohort in phase 1 portion. Lenalidomide is an oral drug supplied in capsules. Administration of Lenalidomide will be in the evening at approximately the same time each day (Days 1-21 followed by 7-day rest). If a dose of lenalidomide is missed or vomited, the patient should continue with the regular schedule of the drug at the next dose, and a missed dose should NOT be made up.

Lenalidomide capsules should be swallowed whole, and should not be broken, chewed or opened. Patients who take more than the prescribed dose of lenalidomide should be instructed to seek emergency medical care if needed and contact study staff immediately.

6.8.2 Dexamethasone Administration

For cycles 1-2 Dexamethasone will be given as a single daily oral dose of 40mg/day on Days 1-4, 9-12, and 17-20. If a dose of dexamethasone is missed or vomited, the patient should continue with the regular schedule of the drug at the next dose.

For cycles beyond 2, dexamethasone 40 mg/day will be given on days 1, 8, 15, and 22.

In the last cohort of 10 patients enrolled in the phase II, who were lenalidomide refractory, dexamethasone will be dosed weekly starting from cycle 1.

Dexamethasone should be taken at approximately the same time each day. Each dose of dexamethasone should be taken with food.

6.8.3 Thalidomide Administration

Thalidomide will be administered orally daily each 28-days cycle. The dose of thalidomide will be specified by each dose level. The dose may be reduced for individual patients in subsequent cycles depending on toxicity. Treatment will be administered on an outpatient basis.

6.8 Concomitant therapy

Lenalidomide and thalidomide both increase the risk of thrombotic events in patients especially in patients who are at high risk or with a history of thrombosis, in particular when combined with other drugs known to cause thrombosis. When lenalidomide and thalidomide is combined with other agents such as steroids (e.g.

dexamethasone, prednisone), anthracyclines (doxil, adriamycin) and erythropoietin the risk of thrombosis is increased.

1. All patients will receive anticoagulation with either low molecular weight heparin (LMWH) (dose adjusted) or warfarin (INR 2-3) if platelets > 50,000. If the platelet count is less than 50,000, and full dose anticoagulation is contraindicated, prophylactic dose of LMWG or aspirin 325 mg po daily may be substituted. For patients who are no longer taking dexamethasone and on maintenance with only single agent therapy may discontinue anticoagulation and use only aspirin.

2. All patients will be given a proton pump inhibitor or H2-blocker for gastric prophylaxis.

6.9 Treatment Compliance

To monitor treatment compliance, reconciliation of lenalidomide and thalidomide capsules will be done at each visit.

6.10 Prohibited concomitant therapy

Concomitant use of other anti-cancer therapies, is not permitted while subjects are receiving study drug during the treatment phase of the study.

6.11 Instructions for dose modifications or interruption during a cycle

Subjects will be evaluated for AEs at each visit with the NCI CTCAE v3.0 used as a guide for the grading of severity. The following tables in Appendix C are suggested modification criteria but not required and dose modification will be physician discretion.

6.12 Discontinuation of Study Treatment

Treatment will continue until the occurrence of any of the following events.

- Disease progression
- Adverse event(s) that, in the judgment of the Investigator, may cause severe or permanent harm or which rule out continuation of the treatment regimen.
- Major violation of the study protocol.
- Withdrawal of consent
- Lost to follow up
- Death
- Suspected pregnancy

Any patient who receives at least one cycle of therapy will be included in the safety analysis.

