4.0 Objectives

Phase 1:

Primary Objectives

1. To determine the maximum tolerated dose (MTD) of the combination of lenalidomide and thalidomide and dexamethasone (LTD) in patients with relapsed/refractory multiple myeloma (RRMM).

Secondary Objectives

1. To determine the Overall response rate (ORR)
2. To determine the Time to progression (TTP)
3. To determine the Progression free survival (PFS)
4. To determine the Time to best response

Phase 2:

Primary objective:

1. To determine the overall (CR + VGPR+ PR) response rate of the combination after 4 cycles of therapy.

Secondary Objectives

1. To determine the CR, VGPR
2. To determine the Time to progression (TTP)
3. To determine the Progression free survival (PFS)
4. To determine the Time to best response
5. To assess the safety of the combination of LTD in patients with RRMM.
6. Time to next therapy
7. Symptom measurement - Multiple-symptom assessment tool

5.1 **Selection of Patients**

5.2 **Inclusion Criteria**

1. Understand and voluntarily sign an informed consent form.
2. Age \geq 18 years at the time of signing the informed consent form.
3. Relapsed/refractory MMM with measurable levels of myeloma paraprotein in serum (\geq 0.5 g/dl), urine (\geq 0.2 g excreted in a 24-hour collection sample), or abnormal free light chain (FLC) ratio.
4. Serum Creatinine \leq 2.5 mg/dl
5. Females of childbearing potential (FCBP)[†] must have a negative serum or urine pregnancy test with a sensitivity of at least 50 mIU/mL within 10-14 days prior to and again within 24 hours of starting lenalidomide and must either commit to continued abstinence from heterosexual intercourse or begin TWO acceptable methods of birth control, one highly effective method and one additional affective method AT THE SAME TIME, at least 28 days before she starts taking lenalidomide. FCBP must also agree to ongoing pregnancy testing. Men must agree to use a latex condom during sexual contact with a female of childbearing potential even if they have had a successful vasectomy. All patients must be counseled at a minimum of every 28 days about pregnancy precautions and risks of fetal exposure. See Appendix A: risks of Fetal Exposure, Pregnancy Testing Guidelines and Acceptable Birth Control methods.

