6.2 Phase I Portion

To determine the MTD of the combination of thalidomide, lenalidomide and dexamethasone (LTD), with 4 dose levels planned. Dosing will start at doses of LTD that are intermediate intensity because of overlapping side effect profile of lenalidomide and thalidomide to determine the MTD and maximize the overall response rate of the regimen.

Table 6-1 Dose Levels to be studied

Dose Level	Assigned Therapy
Level -1	15 mg Lenalidomide daily on days 1-21 followed by 7-day rest every 28 days 50 mg Thalidomide daily 40 mg dexamethasone *
Level 1	15 mg Lenalidomide daily on days 1-21 followed by 7-day rest every 28 days 100 mg Thalidomide daily 40 mg dexamethasone *
Level 2	25 mg Lenalidomide daily on days 1-21 followed by 7-day rest every 28 days 100 mg Thalidomide daily 40 mg dexamethasone *
Level 3	25 mg Lenalidomide daily on days 1-21 followed by 7-day rest every 28 days 200 mg Thalidomide daily 40 mg dexamethasone

* Dexamethasone dosing for cycle 1-2: 40 mg days 1-4, 9-12, and 17-20; all subsequent cycles: 40 mg days 1,8, 15, 21

Dose Escalation

The first cohort of three patients enrolled into the study will receive dose level 1. A full safety evaluation will be conducted when these subjects have completed one cycle (28 days) of combination therapy.

Definition of DLT

A DLT will be defined as follows:

- Hematologic dose-limiting toxicity will be defined as either Grade 4 neutropenia lasting for ≥ 7 days in duration, any Grade 4 thrombocytopenia, or any Grade 5 hematologic toxicity. At least three patients in each cohort must be evaluable for hematologic toxicity.
- Non-hematologic dose-limiting toxicity will be defined as any Grade 3, 4 or 5 non-hematologic toxicity, with the specific exception of:
 - Isolated Grade 3 elevation of liver function tests (LFTs) without associated clinical symptoms, lasting for ≤ 7 days in duration.
 - Isolated Grade 3 elevation of amylase without associated clinical symptoms
 - Grade 3 hypocalcemia, hypokalemia, hypomagnesemia, hyponatremia, or hypophosphatemia which responds to medical intervention.

Definition of Maximum Tolerated Dose:

The MTD of the combination of lenalidomide, thalidomide and dexamethasone in multiple myeloma subjects shall be defined at the end of the trial, the dose with the smallest absolute value of (*posterior mean of pi-pT*) among all the tried doses *i* for which $T_i=0$ will be selected as the MTD.

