7.0 Statistical Consideration

This is an open label, phase I/II clinical trial to evaluate the safety and efficacy of lenalidomide, thalidomide, and dexamethasone in patients with relapsed/refractory multiple myeloma. The maximum number of patients that will be recruited for the study is 64.

Phase I design:

The objective of the phase I portion is to determine the maximum tolerated dose (MTD) of the combination regimen of lenalidomide, thalidomide, and dexamethasone. There are four predefined dose levels for lenalidomide, thalidomide, and dexamethasone, and the first cohort of patients will be treated at the second dose (Dose Level 1).

Dose Level	Assigned Therapy
Level -1	15 mg Lenalidomide daily on days 1-21 followed by 7-day rest every 28 days 50 mg Thalidomide daily 40 mg dexamethasone *
Level 1	15 mg Lenalidomide daily on days 1-21 followed by 7-day rest every 28 days 100 mg Thalidomide daily 40 mg dexamethasone *
Level 2	25 mg Lenalidomide daily on days 1-21 followed by 7-day rest every 28 days 100 mg Thalidomide daily 40 mg dexamethasone *
Level 3	25 mg Lenalidomide daily on days 1-21 followed by 7-day rest every 28 days 200 mg Thalidomide daily 40 mg dexamethasone

Dose limiting toxicity (DLT) is defined as in the treatment plan. To find the MTD, a statistical design based on a Bayesian model described in Ji, Li, and Bekele (2006) will be used. The details of the design are described below.

Let p_i denote the toxicity probabilities for dose $i=1, 2, 3, \text{ and } 4$. The goal is to accurately estimate the probability of toxicity at the current tried dose level. Assuming a vague independent beta prior $B(0.005, 0.005)$ for each p_i , with observed data (n_i, x_i) , where n_i represents the number of patients treated at current dose and x_i represents the number of patients experienced DLTs, the posterior of p_i follows an independent $B(0.005 + x_i, 0.005 + n_i - x_i)$ for $i=1, 2, 3, \text{ and } 4$. Let

$$T_i = 1\{P(p_i > p_T \mid \text{data}) > \xi\}$$

We define the posterior probabilities of three possible actions as

$$q(D, i) = P(p_i > p_T + K_1 \sigma_i \mid \text{data})$$

$$q(S, i) = P(p_T - K_2 \sigma_i \leq p_i \leq p_T + K_1 \sigma_i \mid \text{data})$$

$$q(E, i) = P(p_i < p_T - K_2 \sigma_i \mid \text{data}) * (1 - T_i)$$

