The overall response and toxicity will be monitored simultaneously using the Bayesian approach of Thall, Simon, Estey (1995, 1996) as extended by Thall and Sung (1998). Historical data on similar patients show an overall response rate (ORR) of 30% and toxicity rate of 30%. However, the information was down-weighted to reflect the same marginal ORR and toxicity rates in 2 patients. Independence was assumed between OR and toxicity. It is expected for the current trial that the three-drug combination will improve the ORR to 50% while the toxicity rate is maintained at 40%. A sample size of 36 ensures that, if the trial is not terminated early, a posterior 90% credibility interval for overall response rate will have width of 0.26 at most, under the assumption of a 50% of ORR. The probabilities of OR and toxicity for the historical data are modeled by beta distributions ($Beta(3, 7)$ and $Beta(3, 7)$, respectively). The prior probabilities of OR and toxicity for the experimental regimen are also modeled by beta distributions ($Beta(0.6, 1.4)$ and $Beta(0.6, 1.4)$, respectively), which have the same a/b (a and b denote the parameters for a $Beta$ distribution) ratio as the beta distributions for the historical data. Denoting the historical probabilities of overall response rate and toxicity rate by $\{p(OR,H), p(TOX,H)\}$, the following decision criteria will be applied:

- 1) Let E correspond to the experimental treatment, stop if $\text{Prob}\{p(OR,H) + \delta_{OR} > p(OR,E) | \text{data}\} > 0.90$, where $\delta_{OR} = 0.20$
- 2) Stop if $\text{Prob}\{p(TOX,H) + \delta_{TOX} < p(TOX,E) | \text{data}\} > 0.85$, where $\delta_{TOX} = 0.10$

Patients will be monitored according to the following stopping boundaries for overall response.

Number of patients evaluated	Recommend stopping if \leq OR observed
12	3
24	7
36	11

At the same time, patients will be monitored according to the following stopping boundaries for toxicity.

Among these number of patients	Recommend stopping if \geq toxicity observed
12	8
24	15
36	22

The operating characteristics are summarized in the following table (based on simulations from 10,000 trials).

True Toxicity Rate	True OR Rate	Prob(stop the trial early)
0.1	0.3	0.654
	0.4	0.296
	0.5	0.086

	0.6	0.016
	0.7	0.002
0.25	0.3	0.655
	0.4	0.298
	0.5	0.089
	0.6	0.019
	0.7	0.005
0.4	0.3	0.677
	0.4	0.343
	0.5	0.147
	0.6	0.082
	0.7	0.068
0.55	0.3	0.795
	0.4	0.583
	0.5	0.225
	0.6	0.417
	0.7	0.409

Analysis Plan

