9.3 Adverse Drug Reaction Reporting

Toxicity will be scored using CTCAE Version 3.0 for toxicity and adverse event reporting. A copy of the CTCAE Version 3.0 can be downloaded from the CTEP homepage (<http://ctep.info.nih.gov>). All appropriate treatment areas have access to a copy of the CTCAE Version 3.0. All adverse clinical experiences, whether observed by the investigator or reported by the patient, must be recorded, with details about the duration and intensity of each episode, the action taken with respect to the test drug, and the patient’s outcome. The investigator must evaluate each adverse experience for its relationship to the test drug and for its seriousness.

The investigator must appraise all abnormal laboratory results for their clinical significance. If any abnormal laboratory result is considered clinically significant, the investigator must provide details about the action taken with respect to the test drug and about the patient's outcome.

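### The only safety-analysis set requires at least one cycle of therapy, so on its natural reading it drops treated patients who stop or die in cycle 1, including those who stop for toxicity

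*Combined protocol and SAP*

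**What the plan says.** Section 6.12 lists the events that end treatment and then states: "Any patient who receives at least one cycle of therapy will be included in the safety analysis". The list includes progression, withdrawal of consent, loss to follow-up, death, and "Adverse event(s) that, in the judgment of the Investigator, may cause severe or permanent harm or which rule out continuation of the treatment regimen". None of these requires a completed cycle.

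Section 6.2 gives the length of a cycle when it times the phase I safety evaluation for the point at which the subjects have "completed one cycle (28 days) of combination therapy".

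Other parts of the document bear on safety, but none defines the safety set:

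- **Section 4.0** makes safety a phase II secondary objective: "To assess the safety of the combination of LTD in patients with RRMM".
- **Section 7.0, Phase I design**, has its own denominator. In the dose-finding model, n_i "represents the number of patients treated at current dose".
- **Section 7.0, Phase II design**, says that "patients will be monitored according to the following stopping boundaries for toxicity", with stopping at 8 of 12, 15 of 24 or 22 of 36, but does not say which patients make up those numbers.
- **Section 7.0, Analysis Plan**, names no analysis populations.
- **Section 9.3** covers data capture: "All adverse clinical experiences, whether observed by the investigator or reported by the patient, must be recorded".

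**The concern.** A safety set should be fixed by something known when treatment starts, usually receipt of study drug. This one is fixed by how long the patient stayed on treatment, which toxicity can shorten. A patient who stops for a severe reaction on day 10, or dies in cycle 1, has no stated route into the analysis meant to describe the harm of the combination.

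The plan itself treats cycle 1 as a period of close safety interest. The dose-escalation safety evaluation follows it (section 6.2), and scheduled weekly visits on days 8, 15 and 22 occur only in that cycle (section 6.7).

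The rule also sits badly with the rest of section 7.0. A phase I patient who has a dose-limiting toxicity at the MTD and stops in cycle 1 counts for dose finding and is carried into phase II as one of its first patients, yet falls outside the safety set.

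At stake is the toxicity rate reported for a phase II objective. It is too low if cycle-1 leavers have more toxicity than patients overall, correct if they have the same, and too high if they have less.

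**Working it through.** **Is there another route into the safety set?** The rules for recording and reporting events (sections 8.0, 9.3, 9.4.1 and 9.4.3) ensure that a cycle-1 event is captured. They do not put the patient into a denominator. The phase I count of patients treated applies to dose finding only. The carry-over of MTD patients into phase II says who belongs to phase II, not who is in the safety analysis. So section 6.12 stands alone.

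**Effect on the reported rate.** Let t be the true toxicity rate among all treated patients, e the fraction leaving in cycle 1, and f the share of those leavers who had toxicity. Removing the leavers gives

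reported rate = (t − e·f) / (1 − e).

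The value t = 0.40 is the toxicity rate the plan expects (section 7.0, Phase II design). The documents give neither e nor f; both are assumptions, with e from 5% to 15%. For e = 0.10:

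- f = 1: (0.40 − 0.10)/0.90 = 0.333
- f = 0.75: (0.40 − 0.075)/0.90 = 0.361
- f = 0.40: (0.40 − 0.04)/0.90 = 0.400
- f = 0: 0.40/0.90 = 0.444

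| Share of leavers with toxicity | e = 5% | e = 10% | e = 15% |
|---|---|---|---|
| 100% | 0.368 | 0.333 | 0.294 |
| 75% | 0.382 | 0.361 | 0.338 |
| 40% | 0.400 | 0.400 | 0.400 |
| 0% | 0.421 | 0.444 | 0.471 |

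**Effect on the phase II toxicity stop, only if the boundaries use the 6.12 set.** The plan's own figures come first. Recomputing the posterior probabilities with Beta(0.6, 1.4) for the regimen and Beta(3, 7) for history returns the toxicity boundaries 8/12, 15/24 and 22/36. Exact binomial calculation with looks at 12 and 24 gives an early-stop probability of 0.147 at toxicity 0.40 and response 0.50, and 0.409 at toxicity 0.55 and response 0.70. Both match the plan's table.

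Now take the toxicity rule alone at a true rate of 0.55, the highest in that table:

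P(stop) = P(X₁₂ ≥ 8) + P(X₁₂ < 8 and X₂₄ ≥ 15).

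With all treated patients counted this is 0.304 + 0.103 ≈ 0.408 (unrounded sum). If only patients in the 6.12 set are counted, the reported rate from the formula replaces 0.55. At e = 10% that rate is 0.500, 0.528, 0.550 or 0.611 for f = 1, 0.75, 0.55 or 0.

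| Share of leavers with toxicity | e = 5% | e = 10% | e = 15% |
|---|---|---|---|
| 100% | 0.329 | 0.252 | 0.179 |
| 75% | 0.372 | 0.334 | 0.294 |
| 55% | 0.408 | 0.408 | 0.408 |
| 0% | 0.510 | 0.627 | 0.747 |

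**The case against.** **The sentence guarantees entry to some patients and does not say that only they enter.** This is true of the words. But a threshold has a purpose only if it separates those above it from those below, and nothing else admits those below.

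**Receiving a cycle need not mean completing one.** Section 6.2 speaks of completion and 6.12 does not, so a patient who merely starts cycle 1 might be meant. This is possible. It leaves a rule with two readings and a denominator that could be settled after the data are seen. The same edit cures either case.

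**Section 8.0 plans to rank adverse events by type, frequency and severity with no one-cycle condition, and the logistic regression on toxicity carries none.** Correct, but neither states a population, so neither fills the gap.

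**Nothing ties the phase II boundaries to section 6.12, and phase I patients enter phase II because they were treated at the MTD.** This stands as a limit on scope. The stopping probabilities are conditional for that reason. Equally, nothing says whom the boundaries count.

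**The size is assumed, its direction is not fixed, and it is small beside sampling error.** The first two points stand. On the third, the standard error of a 40% rate in 36 patients is √(0.4 × 0.6/36) ≈ 0.082, a little more than the shift from 40% to 33%. But a larger trial would not average this error away, and the plan can remove it at almost no cost.

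**The events are recorded, and follow-up includes a safety assessment about 30 days after the last dose for anyone who discontinues.** So an omission could be put right at reporting. That makes the fix cheap; it does not make the stated rule sound.

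**Conclusion.** The concern holds. The one stated safety set conditions on reaching a cycle of therapy, an outcome that toxicity itself can prevent, and no other text includes treated patients who fall short.

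If 10% leave in cycle 1, a true 40% toxicity rate is reported as anything from 33% to 44%, depending on how many leavers had toxicity. Over 5% to 15% leaving, the range is 29% to 47%. The downward error, which understates harm, arises when leavers have more toxicity than average. These figures rest on assumed exit rates and toxic shares.

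If, and only if, the phase II toxicity boundaries use this set, the chance of a toxicity stop by 24 patients at a true 55% rate moves from 0.41 to between 0.25 and 0.63 with 10% leaving (0.18 to 0.75 over 5% to 15%). Phase I dose finding and the reporting of individual events are outside the concern. It should be fixed, but it does not undermine the design.

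**What to change.** Replace the sentence in section 6.12 with: *The safety analysis set comprises every patient given at least one dose of any study drug.*

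Add beside the phase II toxicity boundaries in section 7.0: *The toxicity boundaries count this same all-treated set.*

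The first change removes the selection and is worth making by itself. The second settles a denominator that is now unstated.

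The cost is two sentences. No new data collection is needed, because section 9.3 already requires all adverse experiences to be recorded. The one downside is that the reported toxicity rate may be slightly higher.
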